
To further evaluate the efficacy of ruxolitinib cream in participants with moderate AD who had an inadequate response to, or are intolerant to, or contraindicated to TCSs and TCIs (continued).
	
 • Proportion of participants achieving at least a 4-point decrease from baseline in current Itch NRS score at 5, 15, 30, 45, and 60 minutes and 2, 4, and 6 hours post-initial dose on Day 1. • Proportion of participants with EASI50 from baseline at each postbaseline visit. (EASI50 is defined as achieving $\geq 50\%$ improvement in EASI score.) • Proportion of participants with EASI90 from baseline at each postbaseline visit. (EASI90 is defined as achieving $\geq 90\%$ improvement in EASI score.) • Proportion of participants achieving both EASI75 from baseline and IGA-TS at each postbaseline visit. • Change from baseline at each postbaseline visit for the following: 
 – AD-affected %BSA – EASI score – SCORAD score – Itch NRS score – Skin Pain NRS score • Time to open-label escape arm (defined as not achieving 50% improvement in EASI score from baseline at 2 consecutive visits at least 1 week apart) • Proportion of participants concurrently meeting all of the following criteria at each postbaseline visit: IGA score ≥ 3, EASI score ≥ 16, Itch NRS score ≥ 4, BSA $\geq 10\%$, and DLQI score > 10. • Time to concurrently meeting all of the following criteria: IGA score ≥ 3, EASI score ≥ 16, Itch NRS score ≥ 4, BSA $\geq 10\%$, and DLQI score > 10. • Proportion of participants who experience a relapse after study treatment discontinuation. (proportion of participants among EASI75 responders who are on study treatment at Week 24 who meet relapse criteria [loss of EASI50 from baseline] at the safety follow-up visit) • Time to first re-treatment during the VCE period. • Proportion of time off study treatment due to lesion clearance during the VCE period by visit. • Proportion of time on study treatment during the VCE period by visit.

Table 5: Objectives and Endpoints (Continued)

Objectives	Endpoints

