All participants will have a safety follow-up visit 30 days after their Week 24 or ET visit. An exception to this would be for participants who have been in an observation/no treatment period with an IGA score of 0 (clear) from Week 20 or earlier until Week 24; such participants could complete the safety follow-up and Week 24/EOT visits together. In practice, this would mean conducting all Week 24/EOT visit assessments plus the pregnancy test at the Week 24/EOT visit (see Section 8.9.1).

Participants will be assessed for the safety and tolerability of study cream throughout the study by monitoring the type, frequency, and severity of AEs; performing physical examinations; measuring vital signs; and conducting clinical laboratory assessments. Disease severity assessments, including PROs, will also be conducted.

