8.9. Follow-Up

8.9.1. Safety Follow-Up

The safety follow-up period is the interval between the Week 24/EOT or ET visit and the scheduled follow-up visit, which should occur 30 days after the Week 24/EOT or ET visit, with the following 2 exceptions:

- The follow-up visit should occur at the Week 24/EOT visit for participants who have been in an observation/no treatment period with an IGA score of 0 (clear) from Week 20 or earlier until Week 24.
- The follow-up visit should occur 30 days after the last application of study cream if the Week 24/EOT or ET visit was not performed.

New AE and SAEs must be reported up until 30 days after the last application of study cream; ongoing AEs and SAEs must be followed up until toxicities resolve, return to baseline, or are deemed irreversible, whichever is longer. Reasonable efforts should be made to have the participant return for the follow-up visit and report any AEs that may occur during this period.

9. ADVERSE EVENTS: DEFINITIONS AND PROCEDURES FOR RECORDING, EVALUATING, FOLLOW-UP, AND REPORTING

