#### **7.5.2.4. Analysis of Desensitization and Rebound in the VCE DB Period**

The following categorical parameters will be summarized by treatment to assess rebound upon treatment cessation:

- Proportion of participants who experience a relapse after study treatment discontinuation. (ie, proportion of participants among EASI75 responders who are on study treatment at Week 24 who meet relapse criteria [loss of EASI50 from baseline] at the safety follow-up visit)

[figure not shown]
The following endpoints will be summarized by treatment and visit to assess desensitization upon treatment cessation:

[figure not shown]
[figure not shown]
- Proportion of time off study treatment due to lesion clearance during the VCE period by visit
- Proportion of time on study treatment during the VCE period by visit

Time to first re-treatment is defined as the interval between the first interruption due to lesion clearance starting from Week 8 to the end of the VCE period and the time of starting the re-treatment. This analysis will be performed in the VCE re-treatment evaluable population as defined in Section 5.3.7. The Kaplan-Meier estimate of median time to first re-treatment will be presented with its 95% CI. The 95% CI will be calculated using the method by Brookmeyer and Crowley (1982).

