2.9.1	Summary and Analysis of By-Visit EQ-5D-5L VAS Score in the DB Treatment Period	ITT	
2.9.3	Summary of Participants in Each Category of EQ-5D-5L Score in the DB Treatment Period	ITT	

Table No.	Title	Population	Standard
WPAI-AD			
2.10.1	Summary and Analysis of By-Visit WPAI-AD Score in the DB Treatment Period	ITT	
PROMIS			
2.11.1	Summary and Analysis of By-Visit PROMIS Short Form- Sleep-Related Impairment 8a Score in the DB Treatment Period	ITT	
2.11.3	Summary and Analysis of By-Visit PROMIS Short Form- Sleep Disturbance 8b Score in the DB Treatment Period	ITT	
HADS			
2.12.1	Summary and Analysis of By-Visit HADS Score in the DB Treatment Period	ITT	
BSA			
2.13.1	Summary and Analysis of Total %BSA Affected by AD in the DB Treatment Period	ITT	
2.13.3	Summary of By-Visit Change From Baseline in the Number of Intertriginous Regions With Active AD Involvement in the DB Treatment Period	ITT	
Desensitization and Rebound in the VCE DB Period			
2.14.1	Summary and Analysis of Participants Experiencing a Relapse After Study Treatment Discontinuation	Study completers who achieved EASI75 at Week 24 and entered safety follow-up	
2.14.2	Summary and Analysis of Participants' By-Visit Time Off Study Treatment Due to Lesion Clearance During VCE Period	VCE Primary	
2.14.3	Summary and Analysis of Participants' By-Visit Time on Study Treatment During the VCE Period	VCE Primary	
2.14.4	Summary and Analysis of Time to First Re-Treatment During the VCE Period	VCE Re-Treatment evaluable	
Safety			
Exposure			
3.1.1.X	Summary of Exposure During the VC Period	Safety	X
3.1.2	Summary of Exposure (Baseline to Week 24)	Safety	X
3.1.3	Summary of Study Drug Compliance During the VC Period	Safety	X
Adverse Events			
3.2.1.1.X	Overall Summary of Treatment-Emergent Adverse Events in the VC Period	Safety	X
3.2.1.2	Overall Summary of Treatment-Emergent Adverse Events for Participants Who Applied Ruxolitinib Cream Throughout the Study (Baseline to Week 24)	Safety	X
3.2.1.3	Overall Summary of Exposure-Adjusted Treatment-Emergent Adverse Events (Baseline to Week 24)	Safety	X
3.2.2.1.X	Summary of Treatment-Emergent Adverse Events by MedDRA System Organ Class and Preferred Term in the VC Period	Safety	X
3.2.2.2	Summary of Treatment-Emergent Adverse Events by MedDRA System Organ Class and Preferred Term for Participants Who Applied Ruxolitinib Cream Throughout the Study (Baseline to Week 24)	Safety	X

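### The population for SAP Table 2.14.1 omits the condition that relapse is assessed in participants still on study cream at Week 24

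*SAP*

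**What the plan says.** **Endpoint.** Protocol Table 5 defines relapse after stopping treatment as "proportion of participants among EASI75 responders who are on study treatment at Week 24 who meet relapse criteria [loss of EASI50 from baseline" (bracket left open by the excerpt), assessed at the safety follow-up visit. SAP Table 1 carries the same restriction. So does SAP Section 7.5.2.4, which counts EASI75 responders "who are on study treatment at Week 24 who meet relapse criteria" and presents the result as an assessment of rebound when treatment ceases.

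**Planned table.** SAP Appendix A gives the population for Table 2.14.1 as "Study completers who achieved EASI75 at Week 24 and entered safety follow-up". Being on treatment at Week 24 is not required. SAP Section 11.1 records changes from the Protocol: a presentational rewording of the endpoints and clearer definitions of the VCE primary and VCE escape populations. It does not mention the relapse denominator.

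**Follow-up visit.** Protocol Section 8.9.1 makes an exception to the 30-day visit: "The follow-up visit should occur at the Week 24/EOT visit for participants who have been in an observation/no treatment period", provided the IGA score has been 0 from Week 20 or earlier until Week 24. Protocol Section 4.1 words the same exception permissively: "such participants could complete the safety follow-up and Week 24/EOT visits together". It says that in practice this means "conducting all Week 24/EOT visit assessments plus the pregnancy test at the Week 24/EOT visit".

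**The concern.** The endpoint asks what happens to responders when the cream is taken away at Week 24. During the VCE period, being off cream is a planned state: a participant with IGA 0 enters an observation period without treatment. Some EASI75 responders at Week 24 will therefore already have stopped. They have nothing to withdraw at that visit, and the endpoint definition leaves them out for that reason. The table's population line lets them back in.

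The plan then holds two denominators for one endpoint, and nothing says which governs. A programmer working from the population column would produce a different rate from one working from Section 7.5.2.4. For one subgroup the difference has a known direction: a participant whose Week 24 and follow-up visits are the same visit has no later EASI on which to lose response. If counted, such a participant lowers the reported relapse rate without giving any information about rebound.

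**Working it through.** The documents give no relapse rate, denominator or power for this endpoint, so there is no figure to reproduce. The check compares definitions and then works out the consequence under stated assumptions.

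**Step 1. Who is in the table but not in the endpoint?** Divide study completers with EASI75 at Week 24 into three groups.

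| Group | Status at Week 24 | Follow-up EASI | In endpoint (SAP 7.5.2.4)? | In Table 2.14.1 as written? |
|---|---|---|---|---|
| A | On study cream | Separate visit about 30 days later | Yes | Yes |
| B | Off cream, but not meeting the Week 20 exception | Separate visit about 30 days later | No | Yes |
| C | Off cream with IGA 0 since Week 20 or earlier | May be the Week 24 EASI itself | No | Depends on how follow-up entry is read |

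Group B enters the table against the endpoint definition, whatever view is taken of group C. Its members can relapse, but not as a result of stopping at Week 24. The direction of their effect on the rate is unknown.

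**Step 2. Can a combined-visit participant in group C relapse?** Let x be the percentage improvement in EASI from baseline. Entering the table needs x ≥ 75. Relapse needs x < 50. With one EASI reading both conditions apply to the same x, and no value satisfies both. A combined-visit participant in the denominator is always a non-relapser.

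**Step 3. Is group C in the denominator?** The documents support both answers.

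- For inclusion: Protocol Section 4.2 makes the safety follow-up visit part of completing the study, and Section 4.1 treats combined-visit participants as completing both visits together.
- For exclusion: Protocol Section 8.9.1 states that "The safety follow-up period is the interval between the Week 24/EOT or ET visit and the scheduled follow-up visit". A combined visit leaves an interval of zero length, so these participants might be said never to have entered follow-up.

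**Step 4. Size if they are included.** Let s be the share of the table population with a combined visit, and r the relapse rate among everyone else in the table.

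Table rate = r × (1 - s) + 0 × s = r(1 - s)

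Both r and s are assumptions.

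| Assumed r | s = 0% | s = 10% | s = 20% | s = 30% | s = 40% |
|---|---|---|---|---|---|
| 10% | 10% | 9% | 8% | 7% | 6% |
| 20% | 20% | 18% | 16% | 14% | 12% |
| 30% | 30% | 27% | 24% | 21% | 18% |

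For example, 0.20 × (1 - 0.40) = 0.12. If combined-visit participants are excluded, s = 0 and this dilution disappears; group B remains.

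**Step 5. After the fix.** Requiring treatment at Week 24 removes groups B and C. The table then reports the rate in group A. That equals r only if group B is empty or relapses at the same rate as group A.

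**The case against.** The strongest reply is that the governing text is already right. SAP Section 7.5.2.4 and SAP Table 1 both carry the on-treatment condition, and Appendix A says its list of tables serves as a guideline. A programmer who starts from Section 7.5.2.4 produces the intended summary. This limits the consequence but does not remove the conflict. Appendix A waives an SAP amendment only for changes that leave the nature of the analysis alone, and changing who can be counted as a relapser is more than layout.

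Four stronger readings are tempting, and the documents do not support them.

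- **That combined-visit participants definitely count as non-relapsers.** This needs them to pass the follow-up-entry condition, which can be read either way (Step 3). Section 4.1 also makes the combined visit look optional.
- **That everyone off cream at Week 24 dilutes the rate.** Zero relapse is forced only for combined-visit participants. Those who stopped after Week 20 have a separate visit and can relapse.
- **That the ruxolitinib arm is diluted most.** More participants may well be clear on ruxolitinib, but dilution depends on the share within each arm's responders, and the ruxolitinib denominator is larger too. No within-arm share is given. With an assumed r of 30% in both arms, shares of 30% and 10% would show 21% against 27%; exchanging the shares reverses the difference.
- **That escape-arm participants enter the table.** The population line does not exclude them. However, Section 7.5.2.4 and the Appendix A block are both headed as VCE DB analyses, and SAP Section 7.5.2 confines secondary efficacy analyses to the VC and VCE DB periods. Its only exception is IGA-TS and EASI75 in those who entered escape at Week 8. Exclusion is evidently intended; the line could say so.

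**Conclusion.** The mismatch is real and should be corrected. Table 2.14.1 drops a condition that the Protocol and the SAP text both state, and Section 11.1 does not declare a change. As written, the table admits participants who stop nothing at Week 24 into a summary of what happens on stopping.

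The size is conditional. If combined-visit participants are counted, the table rate is r(1 - s): for an assumed r of 20%, between 18% and 12% as s runs from 10% to 40%. If they are not counted, that dilution is nil, and what remains is the inclusion of other off-treatment participants, whose effect on the rate cannot be signed. Neither r nor s comes from the documents, and no difference in bias between the arms can be claimed.

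Relapse is a descriptive secondary endpoint outside the fixed testing sequence. The coprimary and key secondary tests are unaffected.

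**What to change.** Replace the population line for Table 2.14.1 with one that matches SAP Section 7.5.2.4: VCE DB participants (not in the escape arm) with EASI75 at Week 24 who are on study treatment at Week 24 according to the eDiary treatment dates. This also removes combined-visit participants, so no separate rule on visit dates is needed.

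The SAP should say how being on study treatment at Week 24 is derived. Protocol Section 6.1 puts the last possible application on the evening before that visit, so the status has to come from the recorded start and stop dates. The Protocol's two wordings of the combined-visit exception (Sections 4.1 and 8.9.1) should also be reconciled.

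The cost is one population line and a short derivation rule, using dates the Protocol already collects. The downside is a smaller denominator, which will be felt most in the vehicle arm. As a rough guide from the Week 8 planning rates, 225 randomised 2:1 gives 150 and 75 participants, hence 150 × 0.70 = 105 and 75 × 0.15 ≈ 11 EASI75 responders. The documents give no Week 24 rates. A small denominator made up of participants who actually stop treatment answers the question that the endpoint asks.

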10.4.3. Safety Analyses

Safety analyses will be conducted for the safety population.

A TEAE is any AE either reported for the first time or worsening of a pre-existing event after first application of study cream and no later than 30 days after the Week 24 or ET visit. Analysis of AEs will be limited to TEAEs, but data listings will include all AEs regardless of their timing in relation to study cream administration. Adverse events will be tabulated by the MedDRA preferred term and system organ class. Severity of AEs will be based on the National Cancer Institute CTCAE v5.0 using Grades 1 through 5.

The subset of AEs considered by the investigator to have a causal relationship to study cream will be considered treatment-related AEs. If the investigator does not specify the relationship of the AE to study cream, then the AE will be considered treatment-related. The incidence of AEs and treatment-related AEs will be tabulated.

The clinical laboratory data will be analyzed using summary statistics; no formal treatment group comparisons are planned. Laboratory test values outside the normal range will be assessed for severity based on the normal ranges for the clinical reference laboratory. The incidence of abnormal laboratory values and shift tables relative to baseline will be tabulated. Descriptive statistics and mean change from baseline will be determined for vital signs (blood pressure, pulse, respiratory rate, and body temperature) at each assessment time.

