### **5.3.5. Vehicle-Controlled Extension Primary Population**

The VCE primary population includes all participants who entered the VCE period and applied study cream at least once during the VCE DB period. Participants will be analyzed according to the treatment assigned at randomization. For participants who enter the escape arm, only information prior to entry to the escape arm will be presented.

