### **9.2. Adverse Events**

#### **9.2.1. Adverse Event Definitions**

A TEAE is any AE either reported for the first time or worsening of a pre-existing event after first application of study drug and within 30 days after the last dose of study drug. For participants who were initially on vehicle cream and crossed over to the ruxolitinib cream escape arm, the first application date is period specific, and the end date is 30 days after the last application date in this period, or the first application date in the next period, whichever comes first. Analysis of AEs (as discussed below) will be limited to TEAEs, but data listings will include all AEs regardless of their timing in relation to study drug administration.

Adverse events will be tabulated by MedDRA PT and SOC. Severity of AEs will be graded using the National Cancer Institute CTCAE. The CTCAE v5.0 (Grade 1 to 5) is used for this study. The CTCAE reporting guidelines and grading details are available on the Cancer Therapy Evaluation Program website.

The subset of AEs considered by the investigator to be related to study drug will be considered to be treatment-related AEs. If the investigator does not specify the relationship of the AE to study drug, the AE will be considered treatment-related. The incidence of AEs and treatment-related AEs will be tabulated. In addition, serious AEs will also be tabulated.

Any missing onset date, causality, or severity must be queried for resolution. Unresolved missing causality and severity will be handled according to the following rules:

- An unresolved missing causality will be considered treatment-related.
- An unresolved missing severity will be identified as an unknown severity.

For purposes of analysis, all AEs will be considered TEAEs unless the AE can unequivocally be defined as not treatment-emergent.

Application site reactions are AEs that occur at the site of drug application. A summary of ASRs will be provided. Exposure-adjusted summaries will be provided for the safety population, including cumulative TEAEs and cumulative ASRs.

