### **9.2.2. Adverse Event Summaries**

An overall summary of AEs by treatment group will include the following:

- Number (%) of participants reporting any TEAEs
- Number (%) of participants reporting any serious TEAEs
- Number (%) of participants reporting any Grade 3 or higher TEAEs
- Number (%) of participants reporting any treatment-related TEAEs
- Number (%) of participants who temporarily interrupted study drug because of TEAEs
- Number (%) of participants who permanently discontinued study drug because of TEAEs
- Number (%) of participants who had a fatal TEAE

The following summaries will be produced by MedDRA term (if 2 or fewer participants appear in a table, a listing may be appropriate):

- Summary of TEAEs by SOC and PT
- Summary of TEAEs by PT in decreasing order of frequency
- Summary of Grade 3 or higher TEAEs by SOC and PT
- Summary of Grade 3 or higher TEAEs by PT in decreasing order of frequency
- Summary of serious TEAEs by SOC and PT
- Summary of serious TEAEs by PT in decreasing order of frequency

- Summary of treatment-related TEAEs by SOC and PT
- Summary of treatment-related TEAEs by PT in decreasing order of frequency
- Summary of Grade 3 or higher treatment-related TEAEs by SOC and PT
- Summary of treatment-related serious TEAEs by SOC and PT
- Summary of TEAEs leading to temporarily interrupted study drug
- Summary of TEAEs with a fatal outcome by SOC and PT
- Summary of TEAEs leading to interruption of study drug by SOC and PT
- Summary of TEAEs leading to discontinuation of study drug by SOC and PT

Subgroup analysis for TEAEs by age, sex, ethnicity, and region will also be provided.

Adverse events of interest will be summarized in the following categories:

- Cytopenias
  - Anemia
  - Thrombocytopenia
  - Neutropenia
- Herpes zoster
- Viral skin infections
- Nonmelanoma skin neoplasms
- Liver function test elevations
- Malignancies
- Major adverse cardiovascular events
- Venous and arterial thromboembolic events
- Thrombocytosis and elevated mean platelet volume

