3.2.13.2	Summary of Treatment-Emergent Adverse Events Leading to Dose Interruption by MedDRA System Organ Class and Preferred Term for Participants who Applied Ruxolitinib Cream Throughout the Study (Baseline to Week 24)	Safety	X
3.2.14.1.X	Summary of Treatment-Emergent Adverse Events Leading to Discontinuation of Study Drug by MedDRA System Organ Class and Preferred Term in the VC Period	Safety	X
3.2.14.2	Summary of Treatment-Emergent Adverse Events Leading to Discontinuation of Study Drug by MedDRA System Organ Class and Preferred Term for Participants Who Applied Ruxolitinib Cream Throughout the Study (Baseline to Week 24)	Safety	X
3.2.15.X	Summary of Treatment-Emergent Adverse Events of Interest by MedDRA System Organ Class and Preferred Term in the VC period	Safety	X
3.2.16.X	Summary of Treatment-Emergent Adverse Events of Interest by MedDRA Preferred Term in Decreasing Order of Frequency in the VC period	Safety	X
Laboratory			
3.3.1.X	Summary of Laboratory Values – Hematology in the VC Period	Safety	X
3.3.2.X	Summary of Laboratory Values – Chemistry in the VC Period	Safety	X
3.3.3.X	Shift Summary of Hematology Laboratory Values in CTCAE Grade – To the Worst Abnormal Value in the VC Period	Safety	X
3.3.4.X	Shift Summary of Chemistry Laboratory Values in CTCAE Grade – To the Worst Abnormal Value in the VC Period	Safety	X
3.3.5.X	Shift Summary of Hematology Values – To the Worst Abnormal Value in the VC Period	Safety	X
3.3.6.X	Shift Summary of Chemistry Values – To the Worst Abnormal Value in the VC Period	Safety	X
Vital Signs			
3.5.1.X	Summary of Systolic Blood Pressure in the VC Period	Safety	X
3.5.2.X	Summary of Diastolic Blood Pressure in the VC Period	Safety	X
3.5.3.X	Summary of Pulse in the VC Period	Safety	X
3.5.4.X	Summary of Respiratory Rate in the VC Period	Safety	X
3.5.5.X	Summary of Body Temperature in the VC Period	Safety	X

Note: Safety table that ends with X will be repeated for VCE primary population in the VCE DB period, and VCE escape population in the escape arm.

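### Adverse-event tables for the blinded extension give raw percentages although observation time depends on response and is likely to differ between arms; no exposure-adjusted table covers that period

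*SAP*

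**What the plan says.** The note under the table list in SAP Appendix A says: "Safety table that ends with X will be repeated for VCE primary population in the VCE DB period". It covers the adverse-event tables numbered .X, including those for adverse events of interest (3.2.15.X and 3.2.16.X). Their measure is set in SAP 9.2.2, for example "Number (%) of participants reporting any TEAEs".

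Two rules decide how long a participant is observed in these tables.

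- SAP 5.3.5, for the VCE primary population: "For participants who enter the escape arm, only information prior to entry to the escape arm will be presented". This covers escapers from both arms.
- SAP 9.2.1 counts an event as treatment-emergent if it arises "after first application of study drug and within 30 days after the last dose of study drug". For vehicle participants who cross over, the window ends 30 days after the last application in the period, "or the first application date in the next period, whichever comes first". Protocol 10.4.3 sets a different end: "no later than 30 days after the Week 24 or ET visit".

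On exposure adjustment, SAP 9.2.1 says: "Exposure-adjusted summaries will be provided for the safety population, including cumulative TEAEs and cumulative ASRs". The listed outputs are Tables 3.2.1.3 (overall), 3.2.3.3 (by preferred term) and 3.2.3.6 (application site reactions). All three run from baseline to Week 24 and none carries the X, so none is repeated for the blinded extension. No exposure-adjusted table of adverse events of interest is listed for any period.

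**The concern.** A raw percentage compares risk fairly only if the arms are watched for similar times. Here the time is set by the course of the disease. Losing EASI50 leads to escape and ends observation. Clearing (IGA 0) leads to a treatment-free period, and under the SAP a participant who never restarts leaves the window 30 days after the last dose.

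Both routes are likely to be used unequally. The SAP itself compares time to escape between arms by log-rank test (7.5.2.3), and the planning assumptions for Week 8 EASI75 are 70% against 15%. So two mechanisms, pulling in opposite directions and of unknown size, sit inside one percentage. At stake is the reading of the blinded vehicle comparison after Week 8, including uncommon events such as thromboembolism and malignancy. The efficacy conclusions are not touched.

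**Working it through.** The documents state no adverse-event, EASI50 or escape rate, so there is no planned figure to reproduce. The check asks what the tables would show if both arms had the same true event rate.

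**Inputs from the documents.** The extension lasts 16 weeks (112 days) with visits at Weeks 12, 16, 20 and 24. Escape needs a result below EASI50 at two consecutive visits at least 1 week apart, one of which may be unscheduled.

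**Assumptions.** The probability p of first losing EASI50 at a visit is 20% on vehicle and 2% on ruxolitinib (low case 5% and 2%). The common 16-week event risk P is 20% or 40%. The hazard is constant, λ = −ln(1−P)/112 per day.

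**Formulas.** Mean observation = Σ Pr(escape at t) × t + Pr(no escape) × 112. Raw percentage = the same sum with each time t replaced by 1 − exp(−λt).

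**Confirmation at the next scheduled visit** (escape at day 56 or 84 of the extension):

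- Vehicle: 0.20×56 + 0.16×84 + 0.64×112 = 96.3 days.
- Ruxolitinib: 0.02×56 + 0.0196×84 + 0.9604×112 = 110.3 days.
- Shortfall: 1 − 96.3/110.3 = 13%.
- At P = 40% the risks by days 56, 84 and 112 are 22.5%, 31.8% and 40%. Vehicle shows 0.20×22.5 + 0.16×31.8 + 0.64×40 = 35.2%. Ruxolitinib shows 0.02×22.5 + 0.0196×31.8 + 0.9604×40 = 39.5%.

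**Confirmation one week later** (escape at day 35, 63 or 91):

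- Vehicle: 0.20×35 + 0.16×63 + 0.128×91 + 0.512×112 = 86.1 days.
- Ruxolitinib, by the same sum: 109.1 days.
- Shortfall: 21%.

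| Confirmation, 20% vs 2% | Shortfall | Vehicle vs ruxolitinib, P = 20% | Vehicle vs ruxolitinib, P = 40% |
|---|---|---|---|
| Next scheduled visit | 13% | 17.4% vs 19.7% (2.3 points) | 35.2% vs 39.5% (4.3 points) |
| One week later | 21% | 15.6% vs 19.5% (3.9 points) | 31.8% vs 39.1% (7.3 points) |

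At 5% against 2%, the same sums give gaps of 0.4 to 0.7 points at P = 20% and 0.8 to 1.3 at P = 40%. Equal escape in both arms gives a gap of 0.

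**The 30-day tail.** Non-escapers are also observed for 30 days after the last dose; escapers are not. Replacing 112 by 142 for non-escapers in the first case (risk by day 142 is 47.7% at P = 40%) gives 40.1% against 46.9%, so the gap grows from 4.3 to 6.8 points.

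**The opposing mechanism.** Now take a 16-week risk of 25% (λ = 0.0180 per week), the 30-day tail, escapes spread evenly over 4, 8 and 12 weeks, and 10% escape on ruxolitinib. The chance of an observed event is 30.6% for a participant who stays (20.3 weeks). It is 13.2% on average for an escaper, and 13.8% for one whose last application is at week 4 of the extension (8.3 weeks).

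- Ruxolitinib, no early clearance: 0.9×30.6 + 0.1×13.2 = 28.8%.
- Ruxolitinib, 30% clear and never restart: 0.6×30.6 + 0.3×13.8 + 0.1×13.2 = 23.8%.
- Vehicle, 40% escape: 0.6×30.6 + 0.4×13.2 = 23.6%.
- Vehicle, 20% escape: 0.8×30.6 + 0.2×13.2 = 27.1%.

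Without clearance the gaps are +5.2 and +1.7 points. With it they are +0.2 and −3.3, so vehicle can look worse. This case assumes no such clearance on vehicle. It also depends on the SAP's end date: under the protocol's, stopping after clearance does not shorten the window.

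**After the fix.** Events per person-time return λ in both arms whatever the escape split. At P = 25% that is 0.0180 × 52.2 × 100 = 94 per 100 person-years in each arm, so the artificial gap is 0.

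**The case against.** The tables are descriptive, with no between-arm test. The SAP does plan exposure-adjusted tables over 24 weeks, and its wording on them does not exclude others. Treatment duration in the blinded extension (6.4), the number entering escape (6.2) and Kaplan-Meier estimates of time to escape (7.5.2.3) will all be reported, so a careful reader will see an imbalance. Appendix A describes its list as a guideline. The extension is also not a clean randomized comparison: continued blinded treatment depends on EASI50 at Week 8, and the population requires an application in the extension. Exposure adjustment does not repair that selection.

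All of this is true, and it limits the point without removing it. The 24-week tables mix in the first 8 weeks and participants who never reached EASI50. Treatment duration runs to the last application, which is not time in the event window. Escape counts reveal unequal observation but do not correct event percentages for it.

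A reader might go further and infer that only vehicle is cut off, that ruxolitinib must therefore look worse, or that a real excess could never be recognized. The documents support none of these. SAP 5.3.5 truncates escapers in both arms, the SAP window can shorten ruxolitinib observation after clearance, and rates could be derived from data already planned. Nor should escape be placed at the visit where response is first lost: that ignores the confirmation rule and raises the 20% against 2% case to a 24% shortfall and a gap of about 8 points at P = 40%.

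**Conclusion.** The structural point holds. As written, the plan sets raw event percentages side by side for arms whose observation ends for response-dependent reasons, and it lists no rate for that period.

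The direction is conditional and the size is assumed. Without the tail and with the confirmation rule, 20% against 2% loss of response per visit produces an artificial gap of about 2 to 4 points at a 20% event risk and 4 to 7 at 40%. At 5% against 2% it is about 1 point. The tail enlarges the gap; early clearance on ruxolitinib without re-treatment can cancel or reverse it. Because the documents do not settle the sign, neither a gap nor its absence in the raw percentages can be read at face value. This is worth correcting for the safety interpretation.

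**What to change.** In SAP 9.2.1 and Appendix A:

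- Add blinded-extension versions of the exposure-adjusted tables (overall events, by preferred term, application site reactions) and one for adverse events of interest, by randomized arm with 95% CIs.
- Define person-time as running from the start of the blinded extension to the earliest of first event, first escape application or end of the treatment-emergent window. State that time off treatment for clearance inside that window counts as time at risk.
- Reconcile the end of the window between SAP 9.2.1 and Protocol 10.4.3, since it governs the second mechanism.
- Keep the raw percentages as descriptive. Note that the comparison is among Week 8 responders, and that the rates assume a roughly constant hazard and escape unrelated to adverse-event risk.

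The cost is SAP wording and a few more outputs, using a method the SAP already plans and no new data. Vehicle rates may be imprecise. Of about 75 vehicle participants (one third of 225), the 15% EASI75 assumption implies about 11 responders at that level. More would reach EASI50, but no rate is given.
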